# 8.0 Eligibility Screening

- 8.1 Describe screening procedures for determining subjects' eligibility. Screening refers to determining if prospective participants meet inclusion and exclusion criteria.
  - Include all relevant screening documents with your submission (e.g. screening protocol, script, and questionnaire).

# Response:

The screening will be performed 7 days a week and 14 hours a day by the research assistants and coordinator in the emergency department. If a patient is admitted directly to the PICU, the PICU physicians will actively screen patient for eligibility on a 24-hour basis. There will be a screening form to facilitate the screening (attached with this submission).

 $\square$  N/A: There is no screening as part of this protocol.

# 9.0 Recruitment Methods

- □ N/A: This is a records review only, and subjects will not be recruited. NOTE: If you select this option, please make sure that all records review procedures and inclusion/exclusion screening are adequately described in other sections.
- 9.1 Describe when, where, and how potential subjects will be recruited.

*NOTE:* Recruitment refers to how you are identifying potential participants and introducing them to the study. Include specific methods you will use (e.g. searching charts for specific ICD code numbers, Research Participant Groups, posted advertisements, etc.).

# Response:

Most subjects will be recruited in the ED of John R. Oischei Children's Hospital. A research assistant (RA) or the study coordinator will actively screen potential

eligible patients by checking the ED patients' chart in the Kaleida health electronic PowerChart system. A patient with chief complains such as "DKA, hyperglycemia, high blood glucose, fast breathing, weight loss, excessive thirst or peeing" will be screened for eligibility. If a patient is suspected to be eligible for the study, the RA or the coordinator will approach the treating physician, and ask him/her to identify the eligibility of this patient by going over the screening form.

If a patient is directly admitted to the PICU from outside facility, the bedside clinician will screen eligibility by using the screening form.

The screening form is readily available in the PICU and ED for use.

9.2 Describe how you will protect the privacy interests of prospective subjects during the recruitment process.

NOTE: Privacy refers to an individual's right to control access to him or herself.

Response:

If a patient is identified to be eligible for the study in the ED, one of the study PIs or coordinator, or an ED fellow physician will approach the potential subject and his/her legal guardian in the patient's room in the ED and introduce the study to them when no other people are around.

If a patient is identified to be eligible in the PICU, one of the study PIs or the coordinator, or a PICU fellow will approach the potential subject and his/her legal guardian in the patient's room in the PICU and introduce the study to them when no other people are around.

9.3 Identify any materials that will be used to recruit subjects.

*NOTE: Examples include scripts for telephone calls, in person announcements / presentations, email invitations.* 

For advertisements, include the final copy of printed advertisements with your submission. When advertisements are taped for broadcast, attach the final audio/video tape. NOTE: You may submit the wording of the advertisement prior to taping to ensure there will be no IRB-required revisions, provided the IRB also reviews and approves the final version.

Response:

No recruitment materials will be used for this study.

# **10.0 Procedures Involved**

10.1 Provide a description of **all research procedures or activities** being performed and when they are performed once a subject is screened and determined to be eligible. Provide as much detail as possible.

*NOTE:* This should serve as a blueprint for your study and include enough detail so that another investigator could pick up your protocol and replicate the research. For studies that have multiple or complex visits or procedures, consider the addition of a schedule of events table in in your response.

Upon consenting, a copy of the signed informed consent document with the subject name and medical record number will be sent to our inpatient pharmacy by an ED research assistant if the subject is enrolled in the ED. If a subject is enrolled in the PICU, the signed consent will be faxed to the inpatient's pharmacy. Meanwhile, the study protocol will be placed using an electronic order set containing the study DKA management protocol that is identical to the routine management of DKA with the exception of the fluid content per arm. Please refer to study protocol schematic shown in supplement 1.

After receiving the copy of the consent, patients will be randomly assigned a treatment arm (group A or B) and a study ID by the pharmacy following a randomization table generated by a statistician. Each group correlates with a treatment arm assignment visible on a randomization table available only to the inpatient pharmacy personnel. Pharmacy personnel will then provide the appropriate content to the intravenous fluids with a generic label "DKA study fluids with dextrose" and "DKA study fluids without dextrose." The fluids look identical as the bags will be labeled with standardized labelling as "DKA Study fluid with dextrose" or "DKA study fluid without dextrose." The study ID will also be labeled on the bags and typed into the electronic orders by pharmacy. The bags will be properly covered by the labels to ensure complete blinding of the subject and the medical treatment team. The intravenous fluids will be transported to the patients per the regular system used in the ER and PICU.

We anticipate that the eligible patients will be consented within 2 hours of arrival to the PICU or after the first provider makes contact in the ED and shortly thereafter started on continuous infusions of intravenous fluids and insulin per the study protocol.

After admission to the PICU, DKA fluid management uses a two-bag system to maintain glucose levels between 100 and 300 mg/dL. Once the patient's glucose concentration falls below 300 mg/dL, the intravenous fluids containing dextrose are started and the fluids without dextrose are titrated downward. In addition to containing necessary electrolytes, the study intravenous fluids will contain either lactated ringer's or normal saline based on the assigned treatment arm.

Study fluid management of the two-bag system will follow the same guidelines for rate of fluid delivery and amount of dextrose used currently in the routine management of patients in DKA. Bedside healthcare personnel will treat all study subjects identically regardless of treatment arm. To provide blinding to all bedside staff, intravenous fluid bags will be labelled as "DKA study fluid with dextrose" or "DKA study fluid without dextrose." The fluid bags will be covered with an opaque black bag to mask any visible description of the fluid content.

Fluids will be adjusted using the study protocol as outlined here:

Serum Glucose	DKA study fluids without dextrose	DKA study fluids with dextrose	
>300mg/dL	100% of the hourly rate	0%	

200-300 mg/dL	50% of the hourly rate	50% of the hourly rate	
<200 mg/dL	0%	100% of the hourly rate	

Study participants will not receive any additional laboratory tests other than those that are already involved in standard DKA management. Currently, routine DKA management involves hourly finger-stick or laboratory glucose levels, every 2-hour serum electrolytes and blood gases, every 6-hour serum beta-hydroxybutyrate levels, and urine ketones with every void. This will be the same for all study participants on both treatment arms.

The study fluids will be used until the acute management of DKA using the continuous insulin infusion and two-bag fluid system is stopped. This will occur when the venous pH is equal to or greater than 7.30, the serum bicarbonate level is equal to or greater than 15 mmol/L and serum ketone levels are less than 1mmol/L.

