# 2.0 Scientific Endpoints

2.1 Describe the scientific endpoint(s), the main result or occurrence under study.

*NOTE:* Scientific endpoints are outcomes defined before the study begins to determine whether the objectives of the study have been met and to draw conclusions from the data. Include primary and secondary endpoints. Some example endpoints are: reduction of

symptoms, improvement in quality of life, or survival. Your response should **not** be a date.

Response:

The **primary** study outcome will be the duration of metabolic acidosis after hospital admission.

Resolution of metabolic acidosis will be defined in three ways to delineate the iatrogenic effect from intravenous fluids from that of the primary pathology in diabetic ketoacidosis:

- 1. Serum ketone level <1mmol/L;
- 2. Venous pH > 7.3;
- 3. Serum bicarbonate level > 15mmol/L.

**Secondary outcomes**: Length of stay in the pediatric intensive care unit and length of stay in the hospital.

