#### Response:

Baseline demographic data that will be collected including age, sex, race, comorbid conditions, vital signs, number of hospitalizations for DKA in the preceding 12 months, and date and time of transfer to the PICU.

ED lab data that will be collected include all laboratories obtained in the ED, intravenous fluid volume and type administered, time to start of insulin and PRISM score.

PICU lab data that will be collected include all pH, bicarbonate, anion gap, chloride and beta-hydroxybutyrate levels, sodium, potassium, BUN, creatinine, glucose etc. If the patient remains in DKA after 32 hours after initial ED labs, PICU lab data will be collected until the closest to 36 hours after the initial ED labs were obtained.

Outcomes to be collected include length of stay in the hospital and ICU, resolution of acidosis including time to a serum pH>7.30, bicarbonate >15mg/dl, and normal anion gap.

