#### Response:

All the data will be collected from the electronic medical records of enrolled subjects using the Kaleida Health Powerchart system.

10.5 Indicate whether or not **individual** subject results, such as results of investigational diagnostic tests, genetic tests, or incidental findings will be shared with subjects or others (e.g., the subject's primary care physician) and if so, describe how these will be shared.

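### Study fluid stops at pH ≥7.30 and bicarbonate ≥15 mmol/L, but two of the three primary-outcome definitions need values strictly above those limits, so a child stopped exactly on a limit can leave assigned fluid with that definition unmet

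*Combined protocol and SAP*

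**What the plan says.** The stop rule is in Section 10.1. Study fluid runs until the insulin infusion and two-bag system are stopped, which happens when "the venous pH is equal to or greater than 7.30, the serum bicarbonate level is equal to or greater than 15 mmol/L" and serum ketones are below 1 mmol/L, all three together.

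The primary outcome, in Section 2.1, is the duration of metabolic acidosis: "Resolution of metabolic acidosis will be defined in three ways". The ketone definition is below 1 mmol/L, the same as in the stop rule. The other two are "Venous pH > 7.3" and "Serum bicarbonate level > 15mmol/L".

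Section 10.2 repeats the strict operators in its list of outcomes: "time to a serum pH>7.30, bicarbonate >15mg/dl, and normal anion gap". The bicarbonate unit there should be mmol/L.

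On sampling, Section 10.1 describes routine DKA management as including "every 2-hour serum electrolytes and blood gases" and 6-hourly beta-hydroxybutyrate, and adds no tests for the study. Section 11.2 leaves any fluid after the stop to the treating team and runs participation to discharge. No section reconciles the two sets of limits or says how a value on the limit is handled.

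**The concern.** Only the ketone limit agrees between the rule that ends the intervention and the rules that end the primary-outcome clock. For pH and bicarbonate, a value exactly on the limit satisfies the first rule and fails the second. The child then leaves assigned fluid and insulin with the clock still running under that definition. The rest of the recorded duration is accrued off assigned fluid and ends at whatever later draw happens to be taken.

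At stake is the recorded duration for these boundary children under two of the three definitions. Part of it would reflect the choice of operator and the timing of post-stop blood draws rather than the fluid under test.

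**Working it through.** **1. Rules side by side**

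| Marker | Stop rule (10.1) | Resolution (2.1) | Outcome list (10.2) | Agree? |
|---|---|---|---|---|
| Ketones | <1 | <1 | not listed | yes |
| pH | ≥7.30 | >7.3 | >7.30 | no, at 7.30 |
| Bicarbonate | ≥15 | >15 | >15 | no, at 15 |

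**2. Boundary checks.** Each case assumes no earlier higher reading.

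| pH, bicarbonate, ketones | Fluid stops? | Definitions unmet |
|---|---|---|
| 7.30, 16, 0.8 | yes | pH |
| 7.32, 15, 0.8 | yes | bicarbonate |
| 7.30, 15, 0.8 | yes | both |
| 7.31, 16, 0.8 | yes | none |

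A child with an earlier reading above the limit has already met that definition and is unaffected.

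**3. Is the later value captured?** In favour: "PICU lab data that will be collected include all pH, bicarbonate, anion gap, chloride and beta-hydroxybutyrate levels" (Section 10.2), "All the data will be collected from the electronic medical records of enrolled subjects" (Section 10.4), and participation to discharge (Section 11.2). Against: the 2-hourly draws belong to acute DKA management, and no section continues them after the stop. Section 10.2 also ends PICU laboratory collection at the point closest to 36 hours after the first ED labs for a child still in DKA after 32 hours. As an example, such a child who stops on a limit at 34 hours has 36 − 34 = 2 hours of collection left. That is about one further draw, and only if 2-hourly sampling goes on. Capture is possible but not assured.

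**4. How often?** The documents do not give the laboratory reporting unit or recovery rates, so what follows is illustration on assumed inputs.

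Suppose a marker rises steadily by s per hour, is drawn every 2 hours, is reported in units of u, and is the last of the three to clear. It moves 2s between draws, so the first qualifying value falls in a band of width 2s, of which one reporting unit u is recorded as equal to the limit:

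P(stopping value exactly on the limit) = min(1, u/(2s))

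- pH, s = 0.01 per hour: 0.01/0.02 = 50% if u = 0.01; 0.001/0.02 = 5% if u = 0.001.
- Bicarbonate, s = 1.0 mmol/L per hour: 1/2 = 50% if u = 1; 0.1/2 = 5% if u = 0.1.

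When another marker clears last, the chance is lower. A simulation over 64 assumed settings per reporting precision (20,000 children each) gave the share of children stopping with at least one definition unmet. The settings varied recovery rate, the correlation between pH and bicarbonate recovery, ketone clearance time and measurement noise. Only the draw intervals and entry limits come from the protocol.

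| pH unit / bicarbonate unit | Lowest | Median setting | Highest |
|---|---|---|---|
| 0.001 / 0.1 | 0.1% | 1.8% | 7.5% |
| 0.001 / 1 | 0.3% | 5.8% | 25.8% |
| 0.01 / 0.1 | 1.1% | 13.3% | 44.2% |
| 0.01 / 1 | 1.3% | 17.2% | 62.4% |

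The spread from 0.1% to 62.4% shows that the documents do not fix the frequency. None of these figures is an estimate for this trial.

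**5. After the fix.** With ≥ in both places, every set of values that triggers the stop also meets all three Section 2.1 definitions, so the gap is zero.

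**The case against.** The strongest reply is that no rule is broken. Section 10.1 gives a clinical stopping rule and Section 2.1 an analysis endpoint, and nothing says that they must coincide or that duration may be timed only on assigned fluid. Participation runs to discharge, and Section 20.3 continues outcome collection after withdrawal, with permission. Time to the first reading above a limit, compared by randomized arm, is a well-defined quantity. The normal anion gap time in Section 10.2 can already fall after the stop. A delay that affects both arms would largely cancel in the comparison.

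Much of this stands. The protocol states no on-treatment requirement, and the point does not show that the randomized comparison is invalid. What does not stand is that the mismatch is harmless wording. Under the strict definitions, a boundary child's time depends on post-stop draws that the protocol does not guarantee.

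A reader might infer more than the documents support:

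- **The mismatch biases the comparison of arms.** No difference between arms was estimated, and the documents give no basis for one.
- **The delay uses up part of the 8-hour target difference in Section 17.2.** That target is a between-arm contrast. A delay common to both arms cannot be set against it.
- **Outcomes will be missing for a known share of children.** The frequency is unknown, and later values may well be in the record.

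The opposite inference, that the later value is always recoverable, is not supported either, given the 36-hour limit and the silence on post-stop sampling.

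**Conclusion.** The point holds as a minor inconsistency in the primary-endpoint definition. The operator mismatch is certain from the text. The consequence for a boundary child with no earlier higher reading follows by logic: that definition is unmet when assigned fluid ends, and its time is delayed or possibly not captured. The number of children affected cannot be derived, because it depends mainly on reporting precision and also on recovery and ketone clearance rates, none of which is given. No between-arm bias is shown.

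**What to change.** Before outcome data are reviewed, that is, before the first of the 6-monthly interim outcome analyses in Section 19.1, change the endpoint in Sections 2.1 and 10.2 and on the outcomes data form to pH ≥7.30 and bicarbonate ≥15 mmol/L. Correct the bicarbonate unit in Section 10.2 in the same amendment. Changing the endpoint rather than the stop rule leaves clinical management as it is.

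If outcomes have already been reviewed, date the change and report the strict version as a sensitivity analysis from the recorded laboratory values.

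The cost is a small amendment to the primary endpoint, plus that sensitivity analysis if the change comes late. No extra tests or patients are needed. The change does not cover the normal anion gap time, which is not part of the stop rule and can still fall after it.

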#### 10.2 Describe what data will be collected.

*NOTE:* For studies with multiple data collection points or long-term follow up, consider the addition of a schedule or table in your response.

#### Response:

Baseline demographic data that will be collected including age, sex, race, comorbid conditions, vital signs, number of hospitalizations for DKA in the preceding 12 months, and date and time of transfer to the PICU.

ED lab data that will be collected include all laboratories obtained in the ED, intravenous fluid volume and type administered, time to start of insulin and PRISM score.

PICU lab data that will be collected include all pH, bicarbonate, anion gap, chloride and beta-hydroxybutyrate levels, sodium, potassium, BUN, creatinine, glucose etc. If the patient remains in DKA after 32 hours after initial ED labs, PICU lab data will be collected until the closest to 36 hours after the initial ED labs were obtained.

Outcomes to be collected include length of stay in the hospital and ICU, resolution of acidosis including time to a serum pH>7.30, bicarbonate >15mg/dl, and normal anion gap.

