# 3.0 Background

3.1 Provide the scientific or scholarly background, rationale, and significance of the research based on the existing literature and how it will contribute to existing knowledge. Describe any gaps in current knowledge. Include relevant preliminary findings or prior research by the investigator.

Response:

Diabetic Ketoacidosis occurs in approximately 30% of children with new onset type 1 diabetes mellitus (T1DM) and 5-10% of newly diagnosed children with type 2 diabetes [1]. DKA is a decompensated metabolic state resulting from insulin deficiency. DKA is characterized by acidosis, ketonemia, ketonuria, and hyperglycemia. Mortality from DKA in the United States is about 0.15%. Morbidity related to DKA is caused by shock, intestinal ischemia, cardiac arrhythmias, thrombosis, and cerebral edema [2, 3]. Clinically significant cerebral edema occurs in just 0.3-1% of all DKA, but results in 55-87% of all deaths related to DKA. The exact etiology of cerebral edema in DKA remains unclear, but it is consistently associated with osmotic shifts, hypoventilation, cerebral hypoperfusion, and administration of bicarbonate. With the intent to prevent shock, ischemia, and the thrombotic state, providers tend to administer large amounts of intravenous fluids in the form of 0.9% saline, also called normal saline, to patients in the initial treatment of DKA. Aggressive fluid administration has been shown to increase the risk of cerebral edema and does not reverse the primary metabolic deficiency driving the acidosis [4, 5].

During the treatment and recovery phases of DKA, the continued use of aggressive amounts of NS may be the mechanism by which patients develop a hyperchloremic metabolic acidosis (HMA) as NS contains a higher chloride concentration than serum. The detrimental clinical consequences of a high chloride load from intravenous fluids have been demonstrated in patients after trauma, in acute kidney injury, and in certain shock states [6, 7]. During HMA in

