# 6.0 Inclusion and Exclusion Criteria

6.1 Describe the criteria that define who will be **included** in your final study sample.

NOTE: This may be done in bullet point fashion.

Response:

Inclusion criteria:

- 1. Age between 0 and 18 years
- 2. Diagnosis of DKA from Type I DM:
  - a. Venous pH less than 7.25
  - b. Ketonuria as confirmed on urine point-of-care testing or urinalysis
  - c. Hyperglycemia (Serum glucose > 200 mg/dl)
  - d. Serum bicarbonate <15 mmol/L
- 3. Need for PICU admission based on clinical discretion
- 6.2 Describe the criteria that define who will be **excluded** from your final study sample.

*NOTE: This may be done in bullet point fashion.* 

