# Response:

Please find the attached (1) Demographic data form, (2) ER laboratory data form, (3) Outcomes data form, (4) PICU laboratory data form, (5) Screening form

10.4 Describe any source records that will be used to collect data about subjects (e.g. school records, electronic medical records).

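### New-onset versus known diabetes is not named among the baseline data, and no covariate adjustment of hospital stay is planned

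*Combined protocol and SAP*

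**What the plan says.** Section 6.1 requires "Diagnosis of DKA from Type I DM" and sets no condition on whether the diabetes is new or already known. Section 3.1 describes ketoacidosis at first diagnosis. Section 10.2 counts earlier ketoacidosis admissions, which is informative only if known patients also enrol.

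The list in section 10.2 begins "Baseline demographic data that will be collected including age, sex, race, comorbid conditions, vital signs". It continues with the "number of hospitalizations for DKA in the preceding 12 months" and the time of transfer to the PICU. It names no item for new versus known diabetes. Section 10.3 refers to the data form itself ("Please find the attached (1) Demographic data form"), which is not in the available text. Section 10.4 gives the source: "All the data will be collected from the electronic medical records of enrolled subjects".

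Section 2.1 makes PICU stay and "length of stay in the hospital" the secondary outcomes. Aim 2 and the secondary hypothesis (sections 1.1 and 1.2) relate duration of acidosis to both. Section 17.1 compares the arms at baseline by testing and adjusts for any differences found, but only in the analysis of the primary outcome. It names no covariate for either length of stay. Section 10.1 mentions a randomisation table and states no stratification.

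**The concern.** Part of the hospital stay lies outside the reach of the study fluid. Section 11.2 stops the intervention in the PICU before floor transfer but follows the child to discharge. A newly diagnosed child could be expected to stay on for teaching and for starting home insulin, whatever the acidosis does. This is an assumption. If it holds, two analyses are affected.

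- **Stay by arm.** Variation in stay due to onset status becomes noise in the fluid comparison, and a chance imbalance between the arms shifts the estimate.
- **Aim 2.** Duration of acidosis is not randomised, so the allocation does not protect its association with stay. If newly diagnosed children differ in both acidosis duration and stay, the association partly reflects who they are.

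The plan as written offers no remedy in either case, because the variable is not named and no adjustment of stay is foreseen.

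**Working it through.** **1. Can a listed item stand in for onset status?**

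| Child | DKA admissions in the past 12 months |
|---|---|
| Newly diagnosed | normally 0 |
| Known, no recent episode | 0 |
| Known, recent episode | 1 or more |

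A count of 1 or more points to known diabetes, but a count of 0 leaves the status open. Age, sex, race and vital signs do not determine it. The comorbidity item might record known diabetes, but the text does not say so.

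**2. Figures available.** The documents give no SD for length of stay, no share of newly diagnosed children and no difference in stay between the groups, so there is no figure of the plan to reproduce. The 104 children in section 17.2 are calculated for duration of acidosis and do not enter here. The 30% in section 3.1 ("approximately 30% of children with new onset type 1 diabetes mellitus") is the share of newly diagnosed children who present in ketoacidosis. It is not the share of ketoacidosis patients who are newly diagnosed, so it is not used as an input.

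**3. Precision of the arm comparison (illustration).** Assumed inputs: share newly diagnosed p = 0.3 to 0.5; residual SD of stay 24 h; extra stay D = 12, 24 or 48 h.

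- Share of variance explained: R² = p(1−p)D² / [p(1−p)D² + 24²]
- Equivalent gain in sample size: 1/(1−R²) − 1 = p(1−p)D² / 24²

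| D | p | p(1−p)D² | R² | Gain |
|---|---|---|---|---|
| 12 h | 0.3 | 30.24 | 30.24/606.24 = 0.05 | 5% |
| 12 h | 0.5 | 36 | 36/612 = 0.06 | 6% |
| 24 h | 0.3 | 120.96 | 120.96/696.96 = 0.17 | 21% |
| 24 h | 0.5 | 144 | 144/720 = 0.20 | 25% |
| 48 h | 0.3 | 483.84 | 483.84/1059.84 = 0.46 | 84% |
| 48 h | 0.5 | 576 | 576/1152 = 0.50 | 100% |

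The gain formula presumes a linear model for stay. Section 17.1 names no model for stay.

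**4. Chance imbalance (same assumed p).** With 52 per arm, the SE of the difference in the newly diagnosed share is √[2p(1−p)/52], which is 0.090 at p = 0.3 and 0.098 at p = 0.5. Exact binomial calculation puts the chance of an imbalance of at least 10 percentage points at 24-28%, and of at least 20 points at 2-4%. With D = 24 h, a 10-point imbalance shifts the arm difference in stay by 0.10 × 24 = 2.4 h. The 95% range of such shifts is ±1.96 × SE × 24, or about ±4.2 to 4.6 h. With D = 12 h it is about ±2.1 to 2.3 h.

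**5. Aim 2.** Let d be the difference in mean acidosis duration between newly diagnosed and known children, and let D be the difference in stay at a given acidosis duration. Omitting onset status shifts the slope of stay on acidosis duration by D × p(1−p)d / Var(acidosis duration). The shift is zero if d = 0. It inflates a positive association if D and d have the same sign and masks it if they differ. The documents give neither d nor D, so the shift cannot be sized.

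**The case against.** A reader might infer that onset status is not collected and that hospital stay therefore cannot be adjusted for it. The documents do not support that. The list in section 10.2 is introduced as a set of inclusions, not as complete. The demographic form is not available to check. The medical record named in section 10.4 probably shows whether diabetes was known before admission, and the status is fixed before randomisation, so it could be extracted even after enrolment. What stands is that the protocol does not name the item.

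A reader might also infer that onset status is a major driver of stay. No section says so. Section 3.1 links prolonged stay to hyperchloremic acidosis. Every input to the illustration is assumed, and a result running from 5% to 100% is too wide to establish importance.

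Nor is the arm comparison biased. Randomisation balances onset status in expectation, so the cost there is precision and chance imbalance on a secondary outcome. The Aim 2 point is stronger but conditional, since nothing shows that the two groups differ in acidosis duration.

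Finally, the mechanism concerns discharge home. It gives no reason to require the covariate for PICU stay, because section 10.1 ends study treatment on biochemical criteria.

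These objections limit the point without removing it. Even if the form holds the field, section 17.1 still plans no adjustment of stay for any variable.

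**Conclusion.** The point holds as a minor, inexpensive improvement. Three facts rest on the text alone: both groups are eligible, onset status is not named and has no adequate proxy in section 10.2, and section 17.1 plans no covariate adjustment of stay.

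The consequence is conditional. It requires that newly diagnosed children stay longer for reasons other than the fluid and, for Aim 2, that they also differ in acidosis duration. Under the assumed inputs the precision at stake for hospital stay ranges from negligible (12 h extra stay) to a doubling of the effective sample (48 h, half newly diagnosed). The upper end needs an extra stay of two residual SDs and should not be read as an estimate.

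**What to change.** 1. Check the demographic form for a yes/no field 'diabetes newly diagnosed at this admission'. If it is absent, add it, taken from the medical record.
2. In section 17.1, pre-specify that field as a covariate in the analysis of hospital stay by arm and in the Aim 2 association between acidosis duration and hospital stay. Include it regardless of any baseline test. State the model used for stay. Use for PICU stay is optional.

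The cost is one chart item per child, one model term and one line in section 17.1. Enrolment, treatment and laboratory testing do not change.
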